### **5.5. Exploratory Endpoints**

#### **5.5.1. Definitions**

##### **5.5.1.1. Binary Endpoints**

###### **5.5.1.1.1. Liver Stiffness Measurement**

The following liver stiffness measurements (LSM) changes from baseline (in terms of reductions) will be evaluated over time at Week 24, FU Week 24 and FU Week 48:

- $\geq 2$  kPa
- $\geq 4$  kPa
- $\geq 6$  kPa

Only participants from sites with available VCTE (Fibroscan) will be included in the analysis. Within these participants, missing LSM (in kPa) at a specific timepoint will be considered as non-responders for that timepoint. No imputation rule will be used in case of missing data.

#### **5.5.1.1.2. HBV RNA Cut-offs**

The cut-offs for HBV RNA are as follows:

- < LOD
- < LLOQ
- <1000 copies/mL

The cut-offs for HBV RNA change from baseline and RTs are as follows:

- decrease by  $\geq 1.0$  log copies/mL
- decrease by  $\geq 2.0$  log copies/mL
- decrease by  $\geq 3.0$  log copies/mL

#### **5.5.1.1.3. HBcrAg Cut-offs**

The cut-offs for HBcrAg are as follows:

- < 3.0 log U/mL
- < 4.0 log U/mL

The cut-offs for HBcrAg change from baseline and RTs are as follows:

- decrease by  $\geq 1.0$  log U/mL
- decrease by  $\geq 2.0$  log U/mL
- decrease by  $\geq 3.0$  log U/mL

#### **5.5.1.1.4. Anti-HBe Antibodies**

Participants who have positive and negative Anti-HBe values will be evaluated over time.

### **5.5.1.2. Continuous Endpoints**

#### **5.5.1.2.1. Liver Stiffness Measurement**

Severity of liver disease at the end of study intervention and follow-up versus baseline will be evaluated by the changes in fibrosis over time according to Fibroscan LSM.

Change from baseline is defined as the value at a given time point minus baseline value.

#### **5.5.1.2.2. HBV RNA and HBcrAg**

Actual values, changes from baseline (log transformed value) and changes from RTs over time in HBV RNA and HBcrAg will be evaluated.

Change from baseline is defined as the value at a given time point minus baseline value.

The change from baseline value to nadir (i.e. maximum decrease for each participant) in HBV RNA and HBcrAg will be evaluated at 3 intervals: on-treatment nadir (first 24 weeks), during follow-up nadir, and entire study nadir.

#### **5.5.1.2.3. Anti-HBs Antibodies**

Actual values and change from baseline will be evaluated over time when anti-HBs antibodies are assessed.

Change from baseline is defined as the value at a given time point minus baseline value.

#### **5.5.1.3. Time to Event Endpoints**

##### **5.5.1.3.1. Time to First HBV RNA<LOD**

Time to first HBV RNA<LOD is defined as the duration from the date of first study intervention intake to the date of the first occurrence of HBV RNA<LOD (i.e. the date of the first occurrence of HBV RNA<LOD – the date of first study intervention intake + 1). The participants who did not achieve undetectability or who early withdrew from the study before achieving HBV RNA<LOD will be censored at the last HBV RNA assessment before the date of withdrawal.

Time to first HBV RNA<LOD will be also analyzed considering the participants who were retreated with NA before achieving HBV RNA<LOD as censored at the date of NA retreatment.

Only the participants with HBV RNA values  $\geq \text{LOD} + 0.5 \log_{10} \text{ cp/mL}$  (i.e.  $\geq 1.898 \log_{10} \text{ cp/mL}$ ) at baseline will be included in this analysis. Similarly, additional analyses for participants with HBV RNA values  $\geq \text{LOD} + 1.0 \log_{10} \text{ cp/mL}$  and  $\geq \text{LOD} + 2.0 \log_{10} \text{ cp/mL}$ , respectively, will be summarized.

##### **5.5.1.3.2. Time to First HBcrAg Undetectability**

Time to first undetectability of HBcrAg is defined as the duration from the date of first study intervention intake to the date of the first occurrence of undetectability of HBcrAg (i.e. the date of the first occurrence of HBcrAg<LLOQ – the date of first study intervention intake + 1). The participants who did not achieve undetectability or who early withdrew from the study before achieving undetectability of HBcrAg will be censored at the last HBcrAg assessment before the date of withdrawal.

Time to first undetectability of HBcrAg will be also analyzed considering the participants who were retreated with NA before achieving HBcrAg<LLOQ as censored at the date of NA retreatment.

Only the participants with HBcrAg values  $\geq \text{LLOQ} + 0.5 \log_{10} \text{ U/mL}$  (i.e.  $\geq 3.5 \log_{10} \text{ U/mL}$ ) at baseline will be included in this analysis.

##### **5.5.1.3.3. Time to Appearance of Anti-HBs Antibodies**

Appearance of anti-HBs antibodies is defined as a baseline anti-HBs (quantitative) <LLOQ and a post-baseline assessment  $\geq \text{LLOQ}$ .

Time to appearance of anti-HBs antibodies is defined as the time (days) from the date of first study intervention intake to the date of the first occurrence of anti-HBs antibodies appearance + 1. The participants who did not experience emergence of antibodies or who early withdrew from the study before showing emergence of anti-HBs antibodies will be censored at the last anti-HBs antibodies assessment before the date of withdrawal.

Time to appearance of anti-HBs antibodies will be also analyzed considering the participants who were retreated with NA before achieving appearance of anti-HBs antibodies as censored at the date of NA retreatment.

#### 5.5.1.3.4. Time to Appearance of Anti-HBe Antibodies

Appearance of anti-HBe antibodies is defined as a baseline anti-HBe antibodies (qualitative) with a "NEGATIVE" result and a post-baseline assessment with "POSITIVE" result.

Time to appearance of anti-HBe antibodies is defined as the time (days) from the date of first study intervention intake to the date of the first occurrence of anti-HBe antibodies appearance + 1. The participants who did not experience emergence of antibodies or who early withdrew from the study before showing emergence of anti-HBe antibodies will be censored at the last anti-HBe antibodies assessment before the date of withdrawal.

Time to appearance of anti-HBe antibodies will be also analyzed considering the participants who were retreated with NA before achieving appearance of anti-HBe antibodies as censored at the date of NA retreatment.

#### 5.5.1.4. Endpoints for Correlation

##### 5.5.1.4.1. Association Between Baseline Characteristics/Viral Blood Markers and Selected Efficacy Variables

Correlations between baseline characteristics and on-treatment HBV blood markers with off-treatment endpoints will be evaluated. The list of HBV blood markers, including but not limited to, are defined in [Table 6](#).

**Table 6: Pairs of off treatment endpoints and baseline characteristics/on treatment HBV markers**

Off treatment HBV marker	Baseline Characteristics/On treatment HBV marker
HBsAg change from baseline at FU Week 24	
 
• Age
 
• HBsAg value at baseline
 
• HBsAg change from baseline at Week 12
 
• HBsAg change from baseline at Week 24
 
• Treatment failure (Yes; No)
 

HBsAg change from baseline at FU Week 48	
 
• Age
 
• HBsAg value at baseline
 
• HBsAg change from baseline at Week 12
 
• HBsAg change from baseline at Week 24
 
• Treatment failure (Yes; No)
 

HBsAg seroclearance at FU Week 24 (Yes; No)	
 
• Age
 
• HBsAg value at baseline
 
• HBsAg change from baseline at Week 12
 

Off treatment HBV marker	Baseline Characteristics/On treatment HBV marker
	
 
• HBsAg change from baseline at Week 24
 
• Treatment failure (Yes; No)
 

HBsAg seroclearance at FU Week 48 (Yes; No)	
 
• Age
 
• HBsAg value at baseline
 
• HBsAg change from baseline at Week 12
 
• HBsAg change from baseline at Week 24
 
• Treatment failure (Yes; No)
 

NA re-treatment at FU Week 24 (Yes; No)	
 
• Age
 
• HBsAg value at baseline
 
• HBsAg change from baseline at Week 12
 
• HBsAg change from baseline at Week 24
 
• Treatment failure (Yes; No)
 

NA re-treatment at FU Week 48 (Yes; No)	
 
• Age
 
• HBsAg value at baseline
 
• HBsAg change from baseline at Week 12
 
• HBsAg change from baseline at Week 24
 
• Treatment failure (Yes; No)
 

Partial cure at FU Week 24 (Yes; No)	
 
• Age
 
• HBsAg value at baseline
 
• HBsAg change from baseline at Week 12
 
• HBsAg change from baseline at Week 24
 
• Treatment failure (Yes; No)
 

Partial cure at FU Week 48 (Yes; No)	
 
• Age
 
• HBsAg value at baseline
 
• HBsAg change from baseline at Week 12
 
• HBsAg change from baseline at Week 24
 
• Treatment failure (Yes; No)
 

Functional cure at FU Week 24 (Yes; No)	
 
• Age
 
• HBsAg value at baseline
 
• HBsAg change from baseline at Week 12
 
• HBsAg change from baseline at Week 24
 
• Treatment failure (Yes; No)
 

Functional cure at FU Week 48 (Yes; No)	
 
• Age
 
• HBsAg value at baseline
 
• HBsAg change from baseline at Week 12
 
• HBsAg change from baseline at Week 24
 
• Treatment failure (Yes; No)
 

### 5.5.2. Analysis Methods

Summaries and graphs will be provided for each intervention arm and analysis phase, unless specified otherwise.

Statistical comparisons of all exploratory endpoints among intervention arms will be done with no adjustment for multiplicity.

All exploratory endpoints will be analyzed based on the observed case data.

### **5.5.2.1. Binary Endpoints**

#### **5.5.2.1.1. Liver Stiffness Measurement**

The count and proportion of participants who meet those change from baseline thresholds for LSM during the study will be summarized by intervention arm at Week 24, FU Week 24 and FU Week 48.

At each assessment time point, a frequency distribution of severity scores will be produced.

#### **5.5.2.1.2. HBV RNA Cut-offs**

The cut-offs for HBV RNA values and decreases from baseline will be used in separate summaries over time. The count and proportion of participants who meet those HBV RNA thresholds during the study will be summarized descriptively by intervention arm and analysis phase over time, and displayed in graphs like bar charts and/or radar plots.

#### **5.5.2.1.3. HBcrAg Cut-offs**

The cut-offs for HBcrAg values and decreases from baseline will be used in separate summaries over time. The count and proportion of participants who meet those HBcrAg thresholds during the study will be summarized descriptively by intervention arm and analysis phase over time, and displayed in graphs like bar charts and/or radar plots.

#### **5.5.2.1.4. Anti-HBe Antibodies**

The count and proportion of participants with positive and negative anti-HBe values will be summarized descriptively by intervention arm and analysis phase over time.

Shift tables in Anti-HBe positive/negative values from baseline will also be provided at each time point.

### **5.5.2.2. Continuous Endpoints**

The methods of analysis of the continuous exploratory endpoints will be the same as those described in Section [5.4.2.2](#).

#### **5.5.2.2.1. Liver Stiffness Measurement**

The changes from baseline at Week 24, FU Week 24, and FU Week 48 will be summarized using descriptive statistics (n, mean, SE, 90% CI, median, minimum, maximum) by intervention arm. The comparison among intervention arms will be done using ANCOVA with intervention arm, randomization stratification factors as main effects and baseline score as covariate.

Plots of mean (+/- SE) values and changes from baseline over time will be presented. In addition, a waterfall plot will be produced to display the individual changes from baseline in LSM for each participant at a given timepoint.

### **5.5.2.2.2. HBV RNA and HBcrAg**

The actual values, changes from baseline and changes from RTs in HBV RNA and HBcrAg, respectively, will be summarized only descriptively over time in a similar manner as for values and changes from baseline over time in HBsAg, HBeAg, and HBV DNA as described in Section 5.4.2.2.1, including the change from baseline value to nadir (i.e. maximum decrease for each participant) and the various graphical displays.

Waterfall plots for changes from baseline of HBV RNA and HBcrAg will also be presented.

### **5.5.2.2.3. Anti-HBs Antibodies**

The actual values of and changes from baseline in anti-HBs antibodies will be summarized only descriptively in a similar manner as described for values and changes from baseline over time in other blood disease markers in Section 5.4.2.2.1.

For all participants with positive anti-HBs antibodies at baseline who will reach HBsAg seroclearance (as defined in Section 5.4.1.1.4), descriptive statistics will be calculated for the change of anti-HBs antibodies level from baseline at the timepoint when achieving the HBsAg seroclearance. In an additional summary, the change of anti-HBs antibodies level from baseline at the specific timepoint will be summarized descriptively for the subset of the participants achieving HBsAg seroclearance at any time before or at that given timepoint.

Cross-tabulations overtime of quantitative versus qualitative anti-HBs values, respectively, will also be presented.

### **5.5.2.3. Time to Event Endpoints**

The time-to-event endpoints will be analyzed in a similar manner as for the time-to-event endpoints described in Section 5.4.2.3.

### **5.5.2.4. Endpoints for Correlation**

#### **5.5.2.4.1. Association Between Baseline Characteristics/Viral Blood Markers and Selected Efficacy Variables**

Correlations will be evaluated graphically using scatter plots, and heat maps displaying such potential associations.

The following correlation coefficients will be calculated by intervention arm for the different correlation scenarios:

- Pearson's correlation coefficient for two continuous variables.
- Phi correlation coefficient for two binary variables.
- Point biserial correlation coefficient for one binary variable and one continuous variable.

## 5.6. Safety Analyses

Summaries will be provided on the overall population and by intervention arm and analysis phase unless specified otherwise.

Safety and tolerability will be assessed by evaluating treatment emergent-adverse events (TEAEs), physical examinations, ophthalmic examinations, vital signs measurements, clinical laboratory tests (including hematology, blood biochemistry, blood coagulation, and urinalysis), and ECGs.

For all continuous safety variables, descriptive statistics by intervention group will include the N, mean, standard deviation, median, minimum, and maximum. Categorical variables will be summarized by intervention group using frequency counts and percentages.

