Treatment with JNJ-3989 may lead to viral resistance, but resistance to JNJ-3989 is not anticipated to impact treatment with other siRNAs, unless they would have an overlapping trigger binding region. Note that none of the siRNAs in development have overlapping regions. Using these agents in combination, especially in combination with ETV or tenofovir, is expected to minimize the risk of emerging resistant viral variants.

2.3.2.2.2. Potential Risks for Entecavir, Tenofovir Disoproxil, Tenofovir Alafenamide, and PegIFN- α 2a

For the general potential risks of ETV, tenofovir disoproxil, TAF, and PegIFN- α 2a, refer to the respective prescribing information and Summary of Product Characteristics.

Risks specific for this study design are listed below:

- PegIFN- α 2a might increase the immunogenicity of JNJ-3989.
- Combination of PegIFN- α 2a and JNJ-3989 might increase the risk of hematologic abnormalities and/or of bone marrow suppression.

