At regular time points throughout the study (see [Schedule of Activities](#)), blood samples for biochemistry, blood coagulation, and hematology and urine samples for urinalysis, urine chemistry, and renal biomarkers will be collected. Vital signs (systolic and diastolic blood pressure, pulse rate, and body temperature), height (only at screening), body weight, and electrocardiograms (ECGs) will be recorded throughout the study. Physical and ophthalmologic examinations will be performed and AEs will be assessed (see Section 8.2, Safety Assessments). Events of Special Interest will be closely monitored (Section 8.3.6, Adverse Events of Special Interest).

The impact of PegIFN- α 2a addition to JNJ-3989 on ALT elevations is not known in context of HBV monoinfection. Strict rules for management of ALT elevation are in place (refer to Section 8.3.6.2, Intervention-emergent ALT/AST Elevations).

An internal Data Review Committee (DRC) will be established for continuous monitoring of SAEs, AEs leading to discontinuation, and ALT flares to ensure the continuing safety of the participants enrolled in the current study. In addition, an Independent Flare Expert Panel (IFLEP) will be appointed to characterize and adjudicate each ALT flare. See Section 10.3.6, Committees Structure.

Participants will be monitored closely during the 48-week FU Period, with frequent follow-up visits. Participants who completed NA treatment after meeting the NA treatment completion criteria (Section 6.5.1, NA Treatment Completion) based on the Week 24 (EOSI) or FU Week 2 results, should re-start NA treatment if pre-defined NA re-treatment criteria are met (Section 6.5.2, NA Re-treatment Criteria During Follow-up).

JNJ-3989 will be administered using a proper subcutaneous technique to decrease the risk of ISRs. ISRs will be managed as outlined in Section 8.3.6, Adverse Events of Special Interest.

Any clinically significant abnormalities persisting at the end of the study/early discontinuation will be followed up by the investigator until resolution (return to baseline) or until stabilization (to be agreed upon with the Sponsor).

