## 1.2. Study Design

This is a Phase 2, open-label, 3-arm, multicenter study to assess efficacy, safety, tolerability, and pharmacokinetics of treatment with JNJ-3989, NA, and PegIFN- $\alpha$ 2a in long-term ( $\geq 2$  years of NA treatment) virologically suppressed, HBeAg-negative, chronic HBV-infected, adult participants.

Approximately 102 long-term ( $\geq 2$  years of NA treatment) virologically suppressed, HBeAg-negative, chronic HBV-infected, adult participants,  $\geq 18$  (or the legal age of consent in the jurisdiction in which the study is taking place) to 65 years of age (inclusive) will be enrolled in this study.

[figure not shown]
This open-label study will be conducted in 3 periods:

- Screening Period (4 weeks [if necessary, e.g. for operational reasons, can be extended to a maximum of 8 weeks decided on a case-by-case basis and in agreement with the Sponsor]).
- Treatment Period (24 weeks):
  - Arm 1 (N=34): JNJ-3989 for 24 weeks + NA for 24 weeks + PegIFN- $\alpha$ 2a for 24 weeks.
  - Arm 2 (N=34): JNJ-3989 for 24 weeks + NA for 24 weeks + PegIFN- $\alpha$ 2a from Week 12 till Week 24.
  - Arm 3 (N=34): JNJ-3989 for 24 weeks + NA for 24 weeks + PegIFN- $\alpha$ 2a from baseline till Week 12.
- Follow-up (FU) Period (48 weeks), starting at Week 24.

The total duration of individual participation will be up to 72 weeks (screening not included). Participants will be considered to have completed the study if they have completed all the assessments of the end of study (EOS) visit (ie, FU Week 48).

A schematic overview of the trial is presented in [Figure 1](#).

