**Table 3: Analysis Phases Start and End Dates**

Analysis Phase	Start Date	End Date
Screening	The date of signing the informed consent	1 day before the first study agent intake
Treatment period	Date of first study agent intake	
If participant did not withdraw from the study and did not discontinue treatment early prior to the projected/actual Week 24 Visit date:
 
Min [Date of Week 24 study agent intake – 1 day, cut-off dateb]
 
Otherwise:
 
Max [Early study withdrawal visit date, study agent discontinuation date] + 5 daysa or cut-off dateb, whichever occurs first

Follow-up	
Participants who did not withdraw informed consent during treatment period: End of treatment period + 1 day
 
Otherwise: missing
	Max [study discontinuation date, study completion date] or cut-off date b , whichever occurs first

a Addition of 5 days is only applicable for Adverse Events and Concomitant Medications.

b Cut-off dates will be defined to match the prespecified timepoints for DRC safety monitoring, interim analyses, the primary and the final analyses, respectively.

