### **5.1.6. Additional Reference Timepoints**

Three additional Reference Timepoints (RTs) will be used for additional analyses of selected efficacy endpoints.

The PegIFN RT is defined as the last observed non-missing measurement before the first PegIFN- $\alpha$ 2a for Arm 2. This RT will be used for additional analyses for selected efficacy endpoints after Week 12 of treatment period and FU phase.

The NA RT is defined as the last observed non-missing measurement before the start of FU phase for participants who met the NA completion criteria at the EOT. This RT will be used for additional analyses for selected efficacy endpoints for FU phase.

The JNJ-3989 RT is defined as the last observed non-missing measurement at the time of stopping JNJ-3989. This RT will be used for additional analyses for selected efficacy endpoints for FU phase.

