### **5.6.2. Adverse Events**

The verbatim terms used in the CRF by investigators to identify adverse events will be coded using the Medical Dictionary for Regulatory Activities (MedDRA version 21.1 or higher). Any AE occurring at or after the initial administration of study intervention is considered to be treatment emergent. If the event occurs on the day of the initial administration of study intervention, and either event time or time of administration are missing, then the event will be assumed to be treatment emergent. If the event date is recorded as partial or completely missing, then the event will be considered to be treatment emergent unless it is known to be prior to the first administration of study intervention based on partial onset date or resolution date. All reported treatment-emergent adverse events will be included in the analysis. For each adverse event, the number and percentage of participants who experience at least 1 occurrence of the given event will be summarized by intervention arm.

Summary tables will be provided for treatment-emergent adverse events:

- AEs
- Serious AEs (SAEs)
- AEs leading to discontinuation of any study agent within a study intervention including NA
- AEs by relationship to each study agent within a study intervention including NA
- AEs leading to dose interruption/dose modification of each study agent within a study intervention.

In addition to the summary tables, listings will be provided for participants who:

- Had SAEs
- Had AEs leading to discontinuation of each study agent withing a study intervention including NA

For participants reporting rash, a listing with specific grade will be provided.

Incidence of treatment-emergent adverse events of special interest will be summarized by analysis phase and overall

The adverse events of special interest include:

- ALT/AST elevations
- Injection Site Reactions Related to JNJ-3989 and/or PegIFN- $\alpha$ 2a

- Renal Complications
- Hematologic Abnormalities (platelet count, hemoglobin, reticulocytes, neutrophil count)

The list of all preferred terms belonging to ALT/AST elevation, renal complications, and hematologic abnormalities is provided in [Appendix 8](#). Injection site reactions will be identified using the eCRF Injection Site Reaction form.

A listing of participants who died will be provided.

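### Incidence tables for AEs, AEs of special interest and worst laboratory grade run over one 24-week period in which every arm is scheduled for PegIFN, so they do not show the one randomised PegIFN-naive contrast (Arm 2 versus Arms 1 and 3, Weeks 0-12)

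*SAP*

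**What the plan says.** **Reporting unit.** The general safety rule in SAP 5.6 is that "Summaries will be provided on the overall population and by intervention arm and analysis phase unless specified otherwise". Table 3 defines three phases: screening, treatment period and follow-up. The treatment period starts at the "Date of first study agent intake" and runs to Week 24, with no boundary at Week 12.

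**Adverse events.** Under SAP 5.6.2, for each event "the number and percentage of participants who experience at least 1 occurrence of the given event will be summarized by intervention arm". For events of special interest, "Incidence of treatment-emergent adverse events of special interest will be summarized by analysis phase and overall".

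**Laboratory toxicity.** SAP 5.6.3.1 derives the worst grade within each analysis phase, unscheduled assessments included. Treatment-emergent worst grades and abnormalities are tabulated per parameter and phase. The same section also plans laboratory values and changes at scheduled time points, and shift tables over time.

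**Design.** Arm 1 has PegIFN for all 24 weeks. Arm 2 has it "from Week 12 till Week 24". Arm 3 has it for the first 12 weeks (SAP 1.2).

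**Risks named.** Protocol 2.3.3 says that the impact of PegIFN "addition to JNJ-3989 on ALT elevations is not known in context of HBV monoinfection". Protocol 2.3.2.2.2 says that combining PegIFN with JNJ-3989 "might increase the risk of hematologic abnormalities and/or of bone marrow suppression".

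**Use of the PegIFN start in Arm 2.** SAP 5.1.6 says: "The PegIFN RT is defined as the last observed non-missing measurement before the first PegIFN", for Arm 2, and reserves this reference point for selected efficacy endpoints.

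**The concern.** In Weeks 0-12 Arm 2 takes JNJ-3989 and NA alone, while Arms 1 and 3 take the same plus PegIFN. The groups are randomised and concurrent, so this is the natural place to look for a safety effect of adding PegIFN. The planned incidence tables merge those weeks with Weeks 12-24, when Arm 2 is on PegIFN and Arm 3 is off it. Over the whole period Arms 2 and 3 each have 12 weeks on and 12 weeks off, and no arm is unexposed.

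At stake is how clearly the trial reports PegIFN's added risk of cytopenias, ALT elevations and clinical AEs such as neuropsychiatric events. The SAP already relies on this window for efficacy: Section 5.3.6 builds the virtual control from Arm 2's first 12 weeks. For safety, Protocol 9.4.3 plans indirect comparisons across ISAs, although SAP 5.3.6 warns that participants were not randomised across ISAs and that imbalance may bias treatment-effect estimates.

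**Working it through.** The documents give no figure for any safety comparison, so there is none to reproduce. The denominators are the planned ones: 30/(1 - 0.10) = 33.3, rounded up to 34 per arm, and 3 x 34 = 102 (SAP 3).

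**1. Scheduled PegIFN exposure (SAP 1.2)**

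| Arm | n | Weeks 0-12 | Weeks 12-24 |
|---|---|---|---|
| 1 | 34 | on | on |
| 2 | 34 | naive | on |
| 3 | 34 | on | off, after exposure |

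The first half gives 34 naive participants (34 x 12 = 408 person-weeks) against 34 + 34 = 68 on PegIFN.

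**2. Whole-period incidence.** Let q0 and q1 be 12-week incidence off and on PegIFN. Assume constant hazard in each state, no carry-over and full follow-up.

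- Arm 1: 1 - (1 - q1)^2
- Arms 2 and 3: 1 - (1 - q0)(1 - q1), identical whatever the order

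**3. Illustration: q0 = 7%, q1 = 30%.** The 7% is the REEF-1 ALT flare rate at 200 mg (Protocol 2.3.2.2.1), borrowed here as a 12-week rate off PegIFN, which the protocol does not call it. The 30% is assumed.

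- Weeks 0-12: 30 - 7 = 23 points
- 24 weeks, Arm 1: 1 - 0.70^2 = 51.0%
- 24 weeks, Arms 2 and 3: 1 - 0.93 x 0.70 = 34.9%
- 24 weeks, Arms 1+3 minus Arm 2: (51.0 + 34.9)/2 - 34.9 = about 8 points

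**4. Range.** Power is by exact enumeration of a one-sided Fisher test at 0.05, Arm 2 (34) against Arms 1+3 (68). All rates are assumed.

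| Off / on | Weeks 0-12 difference | Power | 24-week difference | Power |
|---|---|---|---|---|
| 7% / 20% | 13 | 44% | 5.2 | 9% |
| 7% / 30% | 23 | 84.5% | 8.0 | 13.9% |
| 7% / 40% | 33 | 98% | 9.9 | 17% |
| 10% / 30% | 20 | 69% | 7.0 | 12% |
| 20% / 30% | 10 | 20% | 3.5 | 6% |

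**5. The most favourable whole-period contrast.** Arms 2 and 3 have equal exposure, so the fairest use of the 24-week tables is Arm 1 against Arms 2+3 (34 versus 68). Take 5% off and 30% on, with Wald 90% half-widths:

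- 24 weeks: 51.0 - (1 - 0.95 x 0.70 = 33.5) = 17.5 points; half-width 1.645 x sqrt(0.510 x 0.490/34 + 0.335 x 0.665/68) = 17.0 points
- Weeks 0-12: 25 points; half-width 1.645 x sqrt(0.30 x 0.70/68 + 0.05 x 0.95/34) = 11.0 points

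With 5% off and 20% on, the figures are 12 +/- 16 and 15 +/- 10 points. These intervals are rough: Arm 2 would expect only 34 x 0.05 = 1.7 events. The two contrasts also estimate different things. The first compares 24 with 12 weeks of PegIFN; the second compares PegIFN with none.

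**6. Limit of the naive group.** With 0 events in 34, the 90% Clopper-Pearson upper limit is 1 - 0.05^(1/34) = 8.4%.

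**The case against.** The strongest reply is that much of the contrast survives in other outputs, and that safety here is descriptive.

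- **Flares.** A reader might infer that flare incidence is buried in the 24-week period too. It is not. SAP 5.4.1.1.14 counts flares while any study intervention, NA included, is being taken. SAP 5.4.1.3.5 and 5.4.2.3 plan Kaplan-Meier cumulative incidence by arm from first intake, so Week 12 flare incidence can be read off. The log-rank test, however, covers the whole window.
- **Laboratory data.** A reader might infer that the contrast is discarded. Scheduled-visit summaries and shift tables keep Weeks 4, 8 and 12. Worst-grade incidence does not.
- **Uniqueness.** Arm 3 is also scheduled PegIFN-free in Weeks 12-24, but after exposure. Arm 2's first half is the only PegIFN-naive window, not the only PegIFN-free one.
- **Whole-period tables.** A reader might infer that they cannot show a PegIFN effect. They retain a randomised 24-versus-12-week contrast, and in one illustration above its interval excludes zero.
- **Ability to estimate.** A reader might infer that the trial cannot state PegIFN's added risk. AE onset dates are collected and nothing bars the table; it is simply not prespecified.
- **DRC.** Reviews start when about half the participants reach Week 4 and recur about every 8 weeks (SAP 5.8.3.1), so early cut-offs hold much PegIFN-free time in Arm 2. They may also include participants past Week 12, so they do not replace a split.
- **Unequal surveillance.** The Week 2 visit is for Arms 1 and 3 only, and PegIFN recipients in Japan have extra visits (Protocol 1.3). A naive Weeks 0-12 count would therefore favour detection on PegIFN, in an open-label trial. This stands and shapes the fix.

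AE tables by relationship to each agent and the protocol's general intention to show safety over time are also planned. The first rests on open-label attribution, and the second is not a specified Week 12 split.

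**Conclusion.** The point holds for AE, special-interest AE and worst-grade laboratory incidence: no planned table sets PegIFN-naive Arm 2 against Arms 1 and 3, although the protocol raises the hematologic and ALT questions. It is a gap in prespecified reporting that data already collected can close, not a flaw that invalidates the safety analysis.

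The size depends wholly on assumed rates, because the documents give none for PegIFN plus JNJ-3989. At 7% versus 30% per 12 weeks, whole-period reporting cuts the Arms 1+3 versus Arm 2 difference from 23 to about 8 points and makes Arms 2 and 3 identical under constant hazards. For smaller effects even the split is weak: 44% power for 7% versus 20%, and 20% for 20% versus 30%. The gain is mainly a cleaner randomised estimate of PegIFN versus none, and only large differences would be detected.

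**What to change.** Keep the whole-phase tables and add the following to the SAP:

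1. Tables by arm for AEs, events of special interest, worst DAIDS grade and treatment-emergent abnormalities, split at Week 12. For Arm 2 the boundary is the first PegIFN dose, or the Week 12 visit if PegIFN is not started. Assign AEs by onset date.
2. One prespecified descriptive difference in incidence, Arms 1+3 versus Arm 2, Weeks 0-12, with a 90% CI by an exact or score method.
3. For the laboratory contrast, only the scheduled visits common to all arms (Weeks 4, 8 and 12). Protocol 1.3 has blood drawn before dosing, so the Week 12 sample belongs to the first sub-period.
4. On-treatment flare incidence at Week 12 by arm, read from the planned Kaplan-Meier analysis.
5. A caveat on the AE contrast for the extra visits on PegIFN and the open-label design.
6. The same outputs for the DRC.

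The cost is SAP wording and more tables, with no new visits or samples. Assigning events by onset date and the small naive group (34) remain limitations.
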